IBP4	Insulin-like growth factor binding protein 4
ITT	Intention to treat
IVH	Intraventricular hemorrhage
LBW	Low birth weight
LC-MS/MS	Liquid chromatography –tandem mass spectrometry
LDA	Low dose aspirin
LMP	Last menstrual period
mg	Milligram
miPTB	Medically-indicated preterm birth
mm	Millimeter
NEC	Necrotizing enterocolitis
NICHD	Eunice Kennedy Shriver National Institute of Child Health and Human Development
NICU	Neonatal Intensive Care Unit
NIH	National Institutes of Health
NMI	Neonatal morbidity and mortality

NNOLOS	Length of neonatal hospital stay (NNOLOS)
NICULOS	Length of neonatal NICU stay (NICULOS)
OHRP	Office of Human Research Protections
P	Probability Value
PECEP	Pesario Cervical para Evitar Prematuridad
PTL	Preterm Labor
PROM	Premature rupture of membranes
PPROM	Preterm premature rupture of membranes
PTB	Preterm birth
PVL	Periventricular leukomalacia
RCT	Randomized Clinical Trial
RDS	Respiratory distress syndrome
RR	Relative Risk
SAE	Serious adverse event
SAB	Spontaneous Abortion
SCF	Specimen Collection Form
SD	Standardized Deviation
SEAR	Statistical analysis plan for health economic analysis of AVERT PTB
SGA	Small for gestational age
SHBG	Sex hormone binding globulin
SOP	Standardized Operating Procedure
SPTB	Spontaneous preterm birth
TOPS	a randomized Trial of Pessary in Singletons
TVCL	Trans-vaginal cervical length
TVUS	Trans-vaginal ultrasound
UAE	Unexpected Adverse Event
UTI	Urinary Tract Infection
VLBW	Very low birth weight
WHO	World Health Organization
17-OHPC	17-hydroxy progesterone caproate

2. Abstract

Executive Summary:

AVERT PRETERM is a historically controlled trial to evaluate the safety and efficacy of a preterm birth (PTB) prevention strategy versus standard-of-care pregnancy management in reduction of the incidence of adverse pregnancy outcomes. Subjects in the prospective arm receive a commercially-available laboratory developed test, PreTRM® (Sera Prognostics, Inc). Those with higher-risk results are offered a multimodal intervention protocol; the remainder receive routine pregnancy management. Outcomes are compared between the prospective arm and historical controls.

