5.7 Exploratory Analyses

In AVERT, there is a challenge and opportunity in the moderate rate of acceptance of intervention among high-scoring women in the intervention arm. The exploratory analyses include options for addressing the non-accepting completers in the prospective arm, and comparing them to those in mITT and the compliant completers.

The exploratory outcomes will be summarized within the prospective arm and within historical controls using descriptive statistics and graphical displays where appropriate. Continuous outcomes will be summarized using sample size (n), means, medians, standard deviations, and ranges. Categorical outcomes will be summarized using frequency and percentages. Estimates will be presented with 95% confidence intervals. Exploratory summaries will be performed for the mITT population.

The following exploratory endpoints will be evaluated by a test of proportions in the prospective arm versus historical controls. The null hypothesis is no difference between historical controls and the prospective arm. The alternative hypothesis is relative reduction in proportion of occurrence of one or more conditions in the prospective arm as compared to historical controls. Statistical testing for these endpoints will be performed using a logistic regression model with covariates as specified above for the primary analysis, and with propensity scoring adjustment as specified for the alternative analysis.

- Reduction in occurrence of one or more major neonatal morbidities with high likelihood of major chronic illness (MNM): cystic periventricular leukomalacia,

- grade 3 and 4 intraventricular hemorrhage, grade 3 or higher retinopathy of prematurity, bronchopulmonary dysplasia.
- Reduction in the rate of PTB <35 weeks, <32 weeks and <37 weeks of gestation. This analysis will be repeated for premature neonates delivered after spontaneous rupture of membranes or spontaneous onset of labor with gestational age at birth <32, <35 and <37 weeks vs. all other neonates.
- Reduction in NICU admission rates in the immediate neonatal period prior to initial discharge or neonatal death. This analysis will be repeated for all premature neonates, and for premature neonates delivered after spontaneous rupture of membranes or spontaneous onset of labor.

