The following exploratory endpoints will be evaluated using a time-to-event analysis. The null hypothesis is no difference between historical controls and the prospective arm. The alternative hypothesis is shorter length of stay in the prospective arm as compared to historical controls. Statistical testing for this endpoint will be performed using a Cox proportional hazards regression model with covariates and stratification as specified above for the primary analysis, and with propensity scoring adjustment as specified for the alternative analysis. Length of hospital stay is adjusted to the maximum observed length of stay plus one for all instances of perinatal mortality. Length of NICU stay is adjusted to the maximum observed length of stay plus one for all instances of NICU mortality.

- Reduction in length of NICU hospital stay of all NICU admissions for premature neonates. For clarity, this analysis includes only PTBs with NICU admission. This analysis will be repeated for all premature neonates delivered after spontaneous rupture of membranes or spontaneous onset of labor.
- Reduction in length of NICU hospital stay (including zero-length stays for those not admitted) for all premature neonates from time of birth up to neonatal discharge. For clarity, this analysis includes PTBs independent of NICU admission, with stays for the non-admitted set to zero days. This analysis will be repeated for all premature neonates delivered after spontaneous rupture of membranes or spontaneous onset of labor.

- Reduction in length of neonatal hospital stay for all premature neonates from time of birth up to neonatal discharge. This analysis will be repeated for all premature neonates delivered after spontaneous rupture of membranes or spontaneous onset of labor.

As exploratory analyses, the primary and alternative analyses will be replicated, with the modification that the exploratory analyses will use multiple imputation and will include the candidate variables for which more than 5% of subjects have a missing value.

As exploratory analyses, the primary analysis will be replicated as a “raw” unadjusted analysis, with the modification that no covariates will be included in regressions.

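### Exploratory stay and NICU-admission tests restricted to preterm infants compare subsets that the strategy itself alters, so the contrasts can be diluted or reversed (minor)

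*SAP*

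**What the plan says.** The SAP's abstract describes the trial as evaluating "a preterm birth (PTB) prevention strategy versus standard-of-care pregnancy management". Section 4 models the treatment effect as a shift in gestational age at birth. Section 5.7 tests preterm birth itself: "Reduction in the rate of PTB <35 weeks, <32 weeks and <37 weeks of gestation".

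The same section then tests the following in preterm infants only:

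- NICU admission, first in all neonates, then: "This analysis will be repeated for all premature neonates, and for premature neonates" delivered after spontaneous rupture of membranes or spontaneous labour.
- NICU stay among preterm infants who were admitted: "For clarity, this analysis includes only PTBs with NICU admission".
- NICU stay among all preterm infants: "this analysis includes PTBs independent of NICU admission, with stays for the non-admitted set to zero days".
- Total stay: "Reduction in length of neonatal hospital stay for all premature neonates from time of birth up to neonatal discharge".

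Each stay endpoint is repeated for spontaneous preterm births. These are tests, not summaries. For the stay endpoints, "The alternative hypothesis is shorter length of stay in the prospective arm as compared to historical controls", by Cox regression. For NICU admission the alternative is a lower proportion, by logistic regression. Section 5.7 has a separate list of outcomes to be described only, and none of these endpoints is on it.

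**The concern.** Membership of the analysis set is settled at birth, or at NICU admission, by events the strategy is meant to prevent. When a late-preterm birth is carried to term, an infant with a short stay leaves the prospective subset, while comparable infants stay in the control subset. What remains in the prospective arm is on average earlier and sicker, even if each remaining infant also gained some gestation. The test restricted to admitted preterm infants selects twice.

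The adjustment variables in section 5.3 are described as present before the blood draw, so neither regression nor weighting on them can undo a selection made months later. Section 6 discusses selection into the study, epoch effects, self-selection into treatment and the pandemic, but not this.

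At stake is how a list of tests labelled as reductions is read. A benefit could be diluted or appear reversed. Conversely, a change that added late-preterm births would look like shorter stays. Section 5.7 also carries the exploratory endpoints into further comparisons (compliant completers, higher-risk against not-higher-risk), so the problem travels with them.

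**Working it through.** The SAP gives no figure for the preterm-only tests, so there is none to reproduce. The check is of direction.

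**When does the preterm-only mean rise?** Let m be the control mean stay among preterm infants, c the share of them carried past 37 weeks, m_c the mean stay those infants would have had, and d the mean reduction among those still preterm. Then

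new preterm mean = m + [c/(1 − c)] × (m − m_c) − d.

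Infants near 37 weeks have short stays, so m − m_c is positive. The preterm mean rises whenever d is less than [c/(1 − c)] × (m − m_c), although every infant is the same or better off.

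**Share of the prospective arm treated.** Section 4 gives a 34% screen-positive rate and 55% compliance. The modified ITT set drops higher-risk women who did not start treatment. Treated share = 0.34 × 0.55 / (0.66 + 0.34 × 0.55) = 0.187/0.847 = 22%. Treated women are at higher risk, so their share of preterm births is larger; 40% is used as an assumed upper case.

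**Simulation 1 (curves assumed, not in the SAP).** 2,000,000 births; 85% Normal(39.2, 1.15) weeks, 15% at 39 minus an exponential with mean 2.3 weeks. Stay = 0.9 × days short of 37.5 weeks if preterm (minimum 2), otherwise 2 days, times lognormal noise (sigma 0.35).

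| Scenario | Preterm rate | Mean stay, all (days) | Preterm-only mean | Preterm-only median |
|---|---|---|---|---|
| Control | 8.6% | 3.27 | 15.4 | 9.6 |
| +1 week if <39 weeks, 22% treated | 7.7% | 3.17 | 15.7 | 9.9 |
| +1 week if <39 weeks, 40% treated | 6.9% | 3.09 | 16.0 | 10.2 |
| Shift 0.15 × (39 − GA), 22% treated | 8.2% | 3.20 | 15.2 | 9.6 |
| Shift 0.15 × (39 − GA), 40% treated | 7.8% | 3.14 | 15.1 | 9.6 |
| Shift 0.15 × (39 − GA), all treated | 6.5% | 2.94 | 14.6 | 9.6 |

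In the third row, preterm days per birth fall from 0.0864 × 15.35 = 1.33 to 0.0689 × 16.04 = 1.11, while the mean per preterm infant rises.

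**Simulation 2 (preterm rate fixed at the SAP's 9.1%, other curves assumed, 40% of pregnancies shifted).**

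| Scenario | Preterm rate | Mean stay, all | Preterm-only stay | NICU days, admitted preterm | NICU admission, preterm |
|---|---|---|---|---|---|
| Control | 9.1% | 3.37 | 17.0 | 23.2 | 64.0% |
| +0.5 week | 8.3% | 3.26 | 17.2 | 23.4 | 64.3% |
| +1 week | 7.7% | 3.18 | 17.4 | 23.7 | 64.8% |
| +2 weeks | 6.8% | 3.08 | 17.9 | 24.1 | 65.7% |
| Larger at early gestation, no birth crosses 37 weeks | 9.1% | 3.19 | 15.1 | 20.8 | 61.3% |

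In every scenario the all-neonate mean improves. The preterm-only figures go either way, according to which births cross 37 weeks.

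**The case against.** The strongest reply is about size. A reader might infer that a strategy that works will look harmful in these tests. The documents do not support that. A large reversal, such as a preterm-only mean of 18.1 days in simulation 1, requires every birth destined for before 39 weeks to be delayed, which halves the preterm rate (8.6% to 4.3%) and ignores the 34% and 55% in section 4. The largest reversal (to about 23.7 days) also confines the benefit to 34–37 weeks, the opposite of section 4, which expects a larger effect at earlier gestation. Under that expected pattern the preterm-only mean falls.

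Nor is a significant finding of harm likely. With 1,453 against 10,000 infants and a rank test standing in for the Cox model, a significantly longer preterm-only stay appeared in about 7–8% of runs for a one-week shift with 22–40% treated, and in 1–3% for the graded shift, against 2.5% by chance. The stated alternative is directional in any case.

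Finally, total stay is co-primary (section 5.5), NICU stay for all neonates is secondary (section 5.6), and NICU admission is tested in all neonates before the preterm repeat. The preterm rate is reported beside them, so a reader can see whether the subset shrank.

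All of this stands, and it limits the severity. It does not make the subsets comparable, and the SAP attaches no caution to them.

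**Conclusion.** The point holds in limited form. Followed as written, these tests compare groups selected after the intervention on outcomes it targets, and the planned adjustment cannot correct that. The likely consequence is a diluted or uninterpretable contrast. Reversal is possible but not expected: about +0.3 to +0.7 days on 15.4 for a one-week shift in 22–40% of births destined for before 39 weeks, against a fall to 14.6–15.2 days if the effect is larger at earlier gestation. These sizes rest on assumed gestational-age and stay curves and on means and medians rather than the specified Cox model; only the direction should be relied on. The all-neonate figures are simple means, whereas sections 5.5 and 5.6 analyse the top quantile of stay. That choice is a separate question, not judged here.

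Severity is minor. The tests are exploratory, outside the Holm procedure, and no success rule depends on them. Nothing here undermines the co-primary or secondary conclusions.

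**What to change.** In section 5.7:

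- Move the preterm-only and NICU-admitted-only stay and admission results, including the spontaneous-birth repeats, to the descriptive list. Give no p-values and no efficacy reading, and state that the subset is selected after the intervention.
- Say that inference on stay and NICU admission rests on the all-neonate comparisons already planned: NNOLOS, NICULOS and the NICU admission rate.
- If a preterm-specific test is wanted, use preterm and NICU-admitted, as a proportion of all neonates, with a spontaneous-preterm version.

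A days-in-hospital endpoint with term births set to zero is not needed; at a 9.1% preterm rate about 91% of its values would be zero, which suits a Cox model poorly.

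The cost is SAP wording and one derived binary variable. The downside is that the contrasts per preterm infant lose their p-values.

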From historical data on pregnancies at ChristianaCare Health System, we estimated a historical preterm birth rate of 9.1%. The sample size estimation is based on simulations of co-primary outcomes based on a simulated distribution of gestational age with a singleton preterm birth rate of 9.1%, and an effect of intervention based on literature data²⁶⁻²⁸, with α -level spending of 0.05 shared between co-primaries using Holm's method.

Given shut-down of the study due to the SARS-CoV-2 pandemic, the sample size for the study is estimated to be approximately 1,453 subjects in the prospective arm, and approximately 10,000 in the historical control group. In the primary and alternative analyses, more than 10,000 subjects may meet the eligibility criteria for the historical control group and have the required data, and if so, they will be included in the study.

Power and sample size for this study are affected by factors including the proportion of prospective subjects receiving PreTRM® risk scores at or above the threshold of 16% risk (the study Screen Positive Rate (SPR)), the proportion of higher-risk subjects complying with interventions (compliance), and the rate at which subjects and their neonates remain in the study (retention). For the purpose of power and sample size estimation and based on study monitoring, we estimate that 34% of subjects in the pre-pandemic portion of the prospective arm had PreTRM® risk scores at or above the threshold of 16% risk (the SPR).

Power and sample size are also affected by the study population's baseline level of risk of adverse neonatal outcomes related to prematurity, the sensitivity of testing in identifying at-risk pregnancies, retention of subjects in the study and the efficacy of the interventions as implemented in the study. Literature²⁶⁻²⁸ indicates that the effect of treatment is not constant across different values of GAB. Thus, there is no single value of the effect size in terms of proportion of subjects with NMI less than 3, or mean length of stay. Rather, the effect size is larger for subjects with earlier GAB, while the effect size is reduced for subjects with later GAB.

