5.1 Analysis Populations

One control population will be considered in primary analyses: the historical control population. The historical control population includes all subjects who attended ChristianaCare during the eligibility period and who satisfy all eligibility criteria.

The historical control arm will be the control population for primary and alternative analysis of the primary, secondary and exploratory endpoints.

Seven subject populations will be considered in the analyses: an Intent-to-Treat (ITT) population, a modified ITT population, a completer(s) population, a compliant completers population, a non-intervention completers population and a safety population. The completers, compliant completers, non-intervention completers and modified ITT populations are subsets of the ITT population.

The ITT population includes all historical subjects selected and all prospective patients enrolled regardless of whether or not the co-primary outcomes were observed, or in the prospective arm, any PreTRM test result has been generated or intervention consent has been signed. Subjects with missing outcomes will be handled as described in the missing data sensitivity analyses.

The modified ITT (mITT) population includes all subjects for whom both co-primary outcomes are known; and who have either been selected for the historical control group, received a not-higher-risk PreTRM® test result, or consented to and initiated treatment before 24^{0/7} weeks gestation after receiving a higher risk PreTRM® test result.

The completers population includes subjects for whom both of the co-primary outcomes are known, and, in the prospective arm, for whom a PreTRM® test result was generated.

The compliant completers population includes ITT subjects who have missed no more than 20% of daily doses for both low-dose aspirin and vaginal progesterone, and participated in weekly care management calls with no more than 20% missed weeks.

The non-intervention completers population includes all ITT subjects who received a higher-risk PreTRM® test result but neither consented to nor initiated treatment before 24^{0/7} weeks gestation.

The safety population includes all eligible subjects who gave consent to participate in the study and attempted a blood draw for the PreTRM® test, regardless of receipt of study interventions.

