5.3 Covariate Analyses

The prospective participants and historical controls in the study may differ in ways other than the interventions or exposures under investigation. Covariates will be used to adjust the regressions prespecified in the primary analysis for potential differences between the control and prospective arms, and in derivation of propensity scores used to adjust for biases between the two arms, either by weighting subjects in the alternative analysis or by matching subjects in exploratory analyses..

The following variables are candidates for inclusion as covariates in the primary analysis: regression with covariates. These baseline covariates are present before blood draw.

- Maternal age
- Categorical parity: multiparous vs. nulliparous
- Maternal substance use disorders assessed as Neonatal Opioid Withdrawal Syndrome

The following variables are candidates for inclusion as covariates in the alternative analysis using inverse probability score weighting, and in the exploratory analysis using propensity matching. These baseline covariates are present before blood draw.

- Maternal age
- Categorical parity (nulliparous vs. multiparous)
- Gravidity (integer)
- Number of term children
- Number of miscarriages
- Maternal race
- Pre-pregnancy continuous BMI
- Pre-pregnancy categorical low BMI<19
- Maternal height
- Maternal chronic hypertension
- Gestational diabetes
- Insurance status
- Smoking status
- Maternal substance use disorders assessed as Neonatal Opioid Withdrawal Syndrome
- Delivery outside of ChristianaCare

Inclusion of covariates in the covariate-adjusted primary, alternative and exploratory analyses will depend on the proportion of missing values for the covariate, as follows. For each candidate variable, if fewer than 1% of subjects have a missing value, that variable will be included as a covariate in the analysis. Sensitivity of results to missing data will be examined using missing data analysis methods.

The primary and alternative analyses will use cases with complete data for the included covariates, provided that no more than 5% of the total subjects are excluded from the analysis. If more than 5% of the total subjects would be excluded from the analysis,

candidate variables will be dropped from the analyses in order of the percent missing, until no more than 5% of the total subjects are excluded from the analysis.

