5.4 Primary and Alternative Analyses

The primary and alternative analyses will be performed in the modified ITT (mITT) population on the primary, secondary and exploratory endpoints.

The primary analysis is regression with covariates as specified for each endpoint.

The alternative analysis is regression with covariates as specified for each primary, secondary and exploratory endpoint, with weighting by inverse propensity score to address potential selection bias.

Propensity-matched and unadjusted “raw” analyses are pre-specified as exploratory analyses. These analyses will be performed on primary and secondary endpoints.

In analysis combining primary, alternative and exploratory analyses, we will present the demographic and baseline characteristics differing between the prospective arm and historical controls, selected from among the covariates prespecified for the primary and alternative analyses. We will compare the primary analysis using prespecified covariates, the alternative analysis using IPW, and exploratory PSM un-adjusted (raw) data analyses (Table 2). The results from these four distinct methods are expected to show similarity in direction and potentially in magnitude of effect. If differences in direction are observed, further analysis such as double robust propensity score analysis will be conducted.

Variable	Covariate Regression			Inverse Probability Weighted			Matched data			Unadjusted “Raw” data		
	Prospective (N=)	Historical (N=)	p-value	Prospective (N=)	Historical (N=)	p-value	Prospective	Historical	p-value			
Age												
Parity												

Table 2: Baseline Characteristics

For pre-specified analysis populations and for subgroups specified under Subgroup Analyses below, analyses will be conducted to examine the clinically important groups and unbalanced variables between the prospective and historical cohorts.

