As an exploratory analysis, a test of the proportional odds assumption for NMI data will be conducted. If the proportional odds assumption does not hold, we will examine the data using a set of separate logistic regressions or partial proportional odds models, to explicitly see how the odds ratios for the explanatory variables vary at the different thresholds. Alternatively, we will also apply the generalized logit model, which treats the response as nominal (unordered) rather than ordinal and has a full set of parameters for each generalized logit. We will then compare the results from proportional, fully nonproportional, and partial proportional odds models fitted to data.

As exploratory analyses, the primary analysis will be replicated, with the modification that the analysis will be restricted to prospective subjects with at least one propensity-matched control, and historical controls will be restricted to those propensity-matched to prospective subjects. At most 4 historical controls will be matched to each prospective subject. Matching algorithms will be chosen from among nearest neighbor matching, caliper matching with comparison units within a certain width of the propensity score of the treated units get matched, where the width is generally a fraction of the standard deviation of the propensity score; Mahalanobis metric matching in conjunction with propensity score matching (PSM), stratification matching, difference-in-differences matching (kernel and local linear weights), or exact matching. The matching method will

be chosen by the distribution of the propensity scores and the balance status of baseline characteristics.

As exploratory analyses, the primary and alternative analyses will be replicated using the ITT population. Subjects with missing data for required variables will be excluded from the analyses. To test if covariates are known to be misclassified under some approaches, an “intention to treat” analysis will be conducted that assumes that each participant continues to be exposed once they have received an initial treatment. Originally used in the analysis of randomized trials, this approach has been used in this hybrid study. It can be worthwhile to do a sensitivity analysis on studies that use an “intention to treat” approach to see how different an “as treated” analysis would be even if intention to treat is the main estimate of interest.

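### The ITT population keeps women whose co-primary outcomes were not observed, but no analysis is specified for them and the ITT replication excludes them

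*SAP*

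**What the plan says.** Section 5.1 defines the ITT population as all historical subjects selected and all prospective women enrolled, "regardless of whether or not the co-primary outcomes were observed". It then states: "Subjects with missing outcomes will be handled as described in the missing data sensitivity analyses".

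The ITT population is used for the endpoints in section 5.7, where the primary and alternative analyses are replicated in it. The rule given there is: "Subjects with missing data for required variables will be excluded from the analyses".

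The main analyses use another population. Section 5.4: "The primary and alternative analyses will be performed in the modified ITT (mITT) population". Section 5.1: "The modified ITT (mITT) population includes all subjects for whom both co-primary outcomes are known". The completers carry the same condition: "The completers population includes subjects for whom both of the co-primary outcomes are known". For covariates, section 5.3 says: "The primary and alternative analyses will use cases with complete data for the included covariates", within a 5% limit on exclusions.

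Multiple imputation appears twice among the analyses of section 5.7: in a replication of the primary and alternative analyses that brings in candidate variables with more than 5% missing, and in the antenatal corticosteroid analysis. Section 5.10 discusses the missing-at-random assumption in general terms, calls multiple imputation and mixed-effects models appropriate under it, and plans a comparison of missingness between the two datasets.

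**The concern.** Two sections give different instructions for the same women. One keeps them for a sensitivity analysis; the other removes them. Only the removal is written in a form that a programmer could carry out.

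An ITT replication exists to show whether the result survives when nobody is dropped for reasons that arise after enrolment. If women with unknown outcomes are dropped, it cannot show that for missing outcomes, although its label says that it does. The co-primary tests are one-tailed for benefit. If women with unknown outcomes did worse than those observed, and this happened more in the prospective arm, the loss would look like benefit and no planned analysis would reveal it.

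Unknown here means truly unobserved. Section 3.7 assigns values to stillbirth and neonatal death (NMI 4, and a length of stay one day above the maximum), so deaths are not the missing cases.

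**Working it through.** **1. Is the promised analysis specified anywhere?**

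- Section 5.7, sensitivity analyses: inclusion and omission of covariates, omission of outliers, bootstrap sampling of controls. None concerns a missing outcome.
- Section 5.10: general remarks and a comparison of missingness by dataset. No imputation of NMI or NNOLOS is set out.
- Section 5.3: sensitivity to missing data is mentioned within the rule for including covariates, with no method named.

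**2. Does the planned imputation reach the outcomes?** The section 5.7 imputation replicates the primary and alternative analyses. Section 5.4 runs these in mITT, and section 5.1 admits to mITT only subjects with both co-primary outcomes known. Nothing is left to impute except covariates. The corticosteroid imputation serves an analysis of steroid timing by group, not the main comparison of the arms.

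**3. Do the other populations retain such women?** Completers need known outcomes by definition. The compliant-completers definition does not state that condition, but its replication also excludes subjects with missing required data. So no specified arm comparison of NMI or NNOLOS keeps a woman with an unknown outcome.

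**4. The plan's own figure.** Section 4 gives power of 0.7 to 0.9 for NMI 3 or more, with 0.036 in controls and 0.023 to 0.02 in the prospective arm. Women leaving mITT by not accepting intervention: 1,453 × 0.34 × 0.45 ≈ 222, leaving 1,231. A one-sided Fisher test at 0.025 (first Holm step), 1,231 against 10,000, gives 0.68 to 0.88, which agrees at one decimal. The power figure is not in dispute. Losing outcomes costs little power: by normal approximation, 10% loss from 1,453 lowers it from 0.753 to 0.707 (rate 0.023) and from 0.928 to 0.901 (rate 0.02). The issue is bias.

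**5. Size of a possible bias.** The SAP gives no missing-outcome rate, so the following are assumptions. Let a share m of prospective outcomes be missing, with k times the observed risk, and no control outcome be missing. True rate = observed rate × [1 + m(k − 1)], so observed/true = 1/[1 + m(k − 1)].

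| m | k | observed/true | understated by |
|---|---|---|---|
| 0.05 | 2 | 1/1.05 = 0.952 | 4.8% |
| 0.05 | 3 | 1/1.10 = 0.909 | 9.1% |
| 0.08 | 2 | 1/1.08 = 0.926 | 7.4% |
| 0.08 | 3 | 1/1.16 = 0.862 | 13.8% |

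The planned relative reduction is 1 − 0.023/0.036 = 36% to 1 − 0.02/0.036 = 44%. In the worst row, an observed 0.023 would be a true 0.023 × 1.16 = 0.0267, a reduction of 26%. An observed 0.02 would be 0.0232, a reduction of 36%.

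**6. Tipping points.** Take 1,453 prospective women including the missing, 360 events in 10,000 controls, and the one-sided Fisher test at 0.025. This is a simplification, because section 5.5 plans a covariate-adjusted ordinal model. The table gives the number of NMI 3 or more cases among the missing women that removes significance.

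| missing | observed rate 0.023 | observed rate 0.02 |
|---|---|---|
| 2% (29) | 5 (17%) | 10 (34%) |
| 5% (73) | 6 (8.2%) | 10 (14%) |
| 10% (145) | 8 (5.5%) | 12 (8.3%) |

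As multiples of the observed rate, the 5% row needs 8.2/2.3 ≈ 3.6 and 13.7/2.0 ≈ 6.8. The 10% row needs 5.5/2.3 ≈ 2.4 and 8.3/2.0 ≈ 4.1.

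**The case against.** Several points on the other side stand.

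- A reader might infer that every planned analysis is complete-case. That is not so: multiple imputation is planned twice in section 5.7. The steroid paragraph could even be read as describing a general scheme for exploratory analyses, namely omission plus an imputed replication. But the ITT paragraph states exclusion and nothing more. The narrower statement, limited to missing co-primary outcomes, is the one that holds.
- A reader might infer that the losses fall mainly in the prospective arm, citing section 4: "more than 10,000 subjects may meet the eligibility criteria for the historical control group and have the required data". That sentence concerns controls beyond about 10,000 in the primary and alternative analyses, whereas the ITT definition covers controls with unobserved outcomes too. Differential loss is plausible, because prospective women are followed from 19 to 20 weeks while controls are identified retrospectively from records. No rate is given for either arm, and section 5.10 leaves the comparison open. Controls selected for having data may hide losses of their own.
- The direction of bias is assumed. Women lost because they delivered elsewhere could be at lower risk. Equal loss at equal relative risk in both arms would cancel in the ratio of rates.
- The sizes are moderate. At 5% missing, losing significance needs more than the assumed two to three times the risk. Only at 10% missing with the weaker effect does about 2.4 times suffice.
- The replication is exploratory and carries no alpha. It is also not the only analysis that restores higher-risk women who declined, since the completers analysis keeps them. The roughly 222 non-acceptors are not missing-outcome losses and should not be counted as such.

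None of this supplies the analysis that section 5.1 promises.

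**Conclusion.** The point holds as a contradiction between sections 5.1 and 5.7, and it rests on no assumed figure. The exclusion rule defeats the plan's own ITT definition, and the imputation that is planned cannot reach a missing co-primary outcome.

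The effect on the result is unknown. Understatement of the prospective rate by about 5% to 14% requires 5% to 8% missing in that arm, none in controls, and two to three times the observed risk among the missing. Alone, that would shrink a 36% to 44% reduction without removing it. The SAP does not show that such a bias exists, in which arm it would lie, or which way it would run. The primary analysis and the stated power are not affected by this point.

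**What to change.** In the section 5.7 ITT replication, stop excluding women because NMI or NNOLOS is missing. Impute both outcomes by multiple imputation, and add a delta-adjusted tipping-point analysis, or a worst-case one, for women with unknown outcomes. Section 5.10 objects that non-ignorable models rest on untestable assumptions. A tipping-point analysis answers this, because it varies the assumption and reports where the conclusion changes.

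Report the number and percentage of missing co-primary outcomes by arm. In section 5.1, replace the general reference to missing-data sensitivity analyses with a reference to this analysis, so that sections 5.1 and 5.7 agree.

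The cost is SAP wording and modest extra programming for an exploratory analysis. No further data collection is needed.
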